## 4.6 Analysis of Safety

All safety data will be reported for the Safety population as per actual study product received. The safety profile of the study treatments will be assessed with respect to AEs, incidents, oral soft tissue (OST) abnormalities and oral hard tissue (OHT) abnormalities.

Safety will be assessed through examination of the subject's oral hard and soft tissues throughout the study, recorded AEs and incidents.

### 4.6.1 Adverse Events and Serious Adverse Events

All AEs will be reviewed by the Clinical Research Scientist or Designee prior to database lock and will be coded to a system organ class (SOC) and preferred term (PT) using the Medical Dictionary for Regulatory Activities (MedDRA).

AEs will be classified as oral and non-oral on the AE page of the electronic case report form (eCRF).

Treatment emergent adverse events (TEAEs) are defined as AEs with an onset date/time on or after the study treatment start date/time (Visit 2). AEs with an onset date prior to the study treatment start date/time (Visit 2) will be considered as non-treatment emergent.

For the assignment of TEAEs, the randomization date will be used as the study treatment start date for subjects randomized to the No Intervention Group.

The following summary tables (by treatment group and overall for subjects in the Safety population) and listings (for all randomized subjects unless otherwise specified) will be presented:

- Table of TEAEs by SOC and PT ([Table 14.3.1.1](#)). Summary of the number and percentage of subjects with at least one TEAE, total number of TEAEs, number and percentage of TEAEs within each SOC and PT will be displayed.
- Table of TEAEs by Oral/Non-Oral and PT ([Table 14.3.1.2](#))
- Table of related TEAEs by Oral/Non-Oral and PT ([Table 14.3.1.3](#))
- Table of AEs related to COVID-19 by SOC and PT ([Table 14.3.1.4](#))
- Listing of all AEs ([Listing 16.2.7.1](#) for all randomized subjects; [Listing 16.2.7.2](#) for non-randomized subjects)
- Listing of all AEs related to COVID-19 Subjects ([Listing 16.2.7.3](#) for all screened subjects)
- Listing of incidents ([Listing 16.2.7.4](#))
- Listing of deaths ([Listing 14.3.2.1](#))
- Listing of non-fatal serious adverse events (SAEs) ([Listing 14.3.2.2](#))
- Listing of TEAEs leading to study or drug discontinuation ([Listing 14.3.2.3](#))
- Listing of TEAEs classified as oral ([Listing 14.3.2.4](#))

Additionally, COVID-19 diagnosis and assessment and the symptoms for symptomatic subjects data will be listed ([Listing 16.2.7.5](#) and [Listing 16.2.7.6](#), respectively) for all screened subjects.

In the event that there is nothing to report, a null table or listing will be produced.

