| To capture photographic images of RPDs for each of the scores in the PDCI scale to assist study site staff with consistent evaluation of the PDCI over the duration of the study, to assist with future studies that might use this scale, and to aid to interpretation of results (including publication of the study outcomes). | Photographs of RPDs.                             |
| Safety   |  |
| To assess the safety and tolerability of a range of dental/denture products when used twice daily for 12 weeks.   | Treatment emergent adverse events and incidents. |

This study will be considered successful if a statistically significant improvement in BI, compared to the no intervention group (existing oral hygiene) at an alpha level of 0.05, is observed following 12 weeks twice daily use of a range of dental/denture products.

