### 8.1 Visit 1/Screening

Screening procedures will be conducted by the Investigator, or suitably qualified designee.

Subjects will be screened within 1-28 days prior to randomization to confirm that they meet the subject selection criteria for the study.

The following Screening procedures will be completed, in the following order (wherever possible), and the findings recorded in the CRF:

Property of GSK Consumer Healthcare - Confidential

May not be used, divulged, published or otherwise disclosed without the consent of GSKCH

SP1963/SOP-208661: Template Version: 14 Mar 2019

1. Informed Consent
2. Demographics
3. Review of medical history (including smoking/tobacco use status) and prior medication/treatment
4. Review of current/concomitant medication
5. Review of dental history
6. Well-fit assessment of the RPD
7. Subject removes RPD
8. Well-made assessment of the RPD
9. Full OST and OHT examinations
10. Gross gingival assessment
11. Review of the inclusion/exclusion criteria
12. Subject eligibility
13. RPD is returned to subject
14. AEs and Incidents recorded

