**Events Meeting the AE Definition:**

- Any abnormal laboratory test results (hematology, clinical chemistry, or urinalysis) or other safety assessments (e.g. ECG, radiological scans, vital sign measurements), including those that worsen from baseline, considered clinically significant in the medical and scientific judgment of the investigator (i.e., not related to progression of underlying disease).
- Exacerbation of a chronic or intermittent pre-existing condition including either an increase in frequency and/or intensity of the condition.
- New conditions detected or diagnosed after study product administration even though it may have been present before the start of the study.
- Signs, symptoms, or the clinical sequelae of a suspected drug-drug interaction.
- Signs, symptoms, or the clinical sequelae of a suspected overdose of either study product or a concomitant medication. Overdose per se will not be reported as an AE/SAE unless it is an intentional overdose taken with possible suicidal/self-harming intent. Such overdoses should be reported regardless of sequelae.
- "Lack of efficacy" or "failure of expected pharmacological action" per se will not be reported as an AE. Such instances will be captured in the efficacy assessments. However, the signs, symptoms, and/or clinical sequelae resulting from lack of efficacy will be reported as AE if they fulfill the definition of an AE.

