## 10.3 Reporting of Adverse Events

### 10.3.1 Reporting Period

All AEs, and therefore all SAEs will be collected immediately after a subject consents to participate in the study by the completion (signature) of the ICF and until 5 days following last administration of the study product (or last procedure).

Property of GSK Consumer Healthcare - Confidential

May not be used, divulged, published or otherwise disclosed without the consent of GSKCH

SP1963/SOP-208661: Template Version: 14 Mar 2019

Medical occurrences that began before obtaining informed consent will be recorded in the Medical History/Current Medical Conditions section of the CRF not the AE section.

Details recorded by the subject on a diary or similar document that meet the definition of an AE must also be discussed with the subjects and transcribed in the AE section of the CRF.

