## 10.6 Follow-up of Adverse Events

After the initial report, the investigator is required to proactively follow up with each subject and provide further information on the subject's condition.

All AEs (serious and non-serious) will be followed until resolution, until the condition stabilizes, until the event is otherwise explained, or until the subject is lost to follow-up.

The investigator is obligated to perform or arrange for the conduct of supplemental measurements and/or evaluations as may be indicated or as requested by GSK CH to elucidate as fully as possible the nature and/or causality of the AE. This may include additional laboratory tests or investigations, histopathological examinations, or consultation with other health care professionals.

New or updated information will be recorded on the AE CRF page and on the SAE form (subject to the classification of the AE).

The investigator will submit any updated SAE data to GSK CH within 24 hours of receipt of the information.

Investigators are not obliged to actively seek AEs in former subjects. However, if the investigator learns of a SAE, including death, at any time after a subject has been discharged from the study, and considers the event reasonably related to the study product or study participation, the investigator will promptly notify GSK CH by emailing the information to the GSK CH Clinical Operations Safety Reporting email box [PPD](#).

The GSK CH Study Manager or designee will be responsible for forwarding the information to the Case Management Group, Global Clinical Safety and Pharmacovigilance group mailbox at [GSK PPD](#)

The investigator will submit any updated SAE data to GSK CH within the designated reporting time frames.

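### The SAP's treatment-emergent rule looks only at onset date, so an adverse event open at Visit 2 that worsens on product may be missed in the TEAE outputs, depending on an unstated recording rule

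*SAP*

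**What the plan says.** Protocol Table 3-1 gives the safety endpoint as "Treatment emergent adverse events and incidents". Protocol 12.2.7 says that TEAEs will be summarised but does not define them, so the definition rests on SAP 4.6.1. That section makes an AE treatment-emergent when its onset is at or after study treatment start at Visit 2. It then states the converse: "AEs with an onset date prior to the study treatment start date/time (Visit 2) will be considered as non-treatment emergent". For the control arm, "the randomization date will be used as the study treatment start date for subjects randomized to the No Intervention Group". SAP Table 5-1 lists no change on this point.

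Three protocol rules bear on the definition:

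- Section 10.3.1: "All AEs, and therefore all SAEs will be collected immediately after a subject consents to participate in the study". Section 8.1 sets the interval: "Subjects will be screened within 1-28 days prior to randomization".
- Section 10.1 lists among events that meet the AE definition: "Exacerbation of a chronic or intermittent pre-existing condition including either an increase in frequency and/or intensity of the condition". Section 9.3.1 also has worsening of an oral soft tissue (OST) finding since Screening recorded as an AE, and section 9.3.2 does so for any oral hard tissue (OHT) change.
- Section 10.6, on follow-up: "New or updated information will be recorded on the AE CRF page and on the SAE form".

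**The concern.** The protocol treats worsening as a harm in its own right. The SAP definition does not carry this through for an AE that began between consent and Visit 2. For such an AE the definition looks at when it began, not at what happened to it on product.

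Pre-treatment AEs are to be expected in this design. Visit 2 includes a full OST examination before randomization and first product use, and an abnormality new since Screening is recorded as an AE.

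What is at stake is the by-arm count of the named safety endpoint and two listings limited to TEAEs: events leading to discontinuation (14.3.2.3) and oral events (14.3.2.4). Worsening of an oral lesion is a plausible event here, since the foam instructions in Protocol 15.2 warn of mucous membrane irritation.

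**Working it through.** No figure in the plan can be reproduced on this point. The check is a comparison of the texts, followed by the one piece of arithmetic that the documents allow.

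**Step 1. Apply the rule to cases.** Take a mild mouth ulcer that becomes severe on Day 10 of product use.

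| Case | Ulcer begins | How the worsening is recorded | Onset used | Class under SAP 4.6.1 |
|---|---|---|---|---|
| A1 | Day -5, after consent | Open AE record updated, onset unchanged | Day -5 | Not a TEAE |
| A2 | Day -5, after consent | Separate AE record | Day 10 | TEAE |
| B | Before consent, so medical history (Protocol 10.3.1) | New AE, as an exacerbation (Protocol 10.1) | Day 10 | TEAE |
| C | Day 10, new severe ulcer | New AE | Day 10 | TEAE |

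A1 and A2 are the same clinical event and differ only in data entry. A1 and B follow the same course on product and differ only in whether the ulcer began before or after consent.

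**Step 2. Ask which of A1 and A2 the documents require.** Protocol 10.6 sends new or updated information to the AE page of the CRF. It does not say that this is the existing entry or that the onset is kept, but it allows that reading. Protocol 9.3.1, 9.3.2 and 10.1 allow a separate AE, and none of them says what to do when an AE record is already open. The CRF completion rules are not in either document. The question is therefore open.

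**Step 3. Trace the outputs for A1** (SAP 4.1.1, 4.6.1 and 4.6.2).

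- Absent: Tables 14.3.1.1, 14.3.1.2 and 14.3.1.3, and Listings 14.3.2.3 and 14.3.2.4.
- Present: Listing 16.2.7.1 (all AEs); Listing 14.3.2.1 or 14.3.2.2 if fatal or serious; Table 14.1.1 and Listing 16.2.1.1 if the subject withdraws; and the OST or OHT examination listings (16.2.8.1, 16.2.8.2) for oral findings.
- Uncertain: OST shift Table 14.3.4.1. Baseline is the pre-treatment assessment at Visit 2 (SAP 3.1), and OST results are coded normal or abnormal (Protocol 9.3.1). On that coding, a lesion present at Visit 2 that worsens goes from abnormal to abnormal and shows no shift.

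**Step 4. Size of the exposed window.** The inputs are a pre-treatment interval of 1 to 28 days (Protocol 8.1), nominal treatment to Day 84 (Protocol Table 1-1), and collection for 5 days after the last administration or procedure (Protocol 10.3.1).

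Share = pre-treatment days / (pre-treatment days + 84 + 5)

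- Shortest: 1 / (1 + 84 + 5) = 1/90 = 1.1%
- Longest: 28 / (28 + 84 + 5) = 28/117 = 23.9%

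At a constant AE rate (an assumption), this is the share of AEs that start before treatment. The share at risk of misclassification is this figure multiplied by the proportion that later worsen, which the documents do not give. As an illustration only, an assumed 5% to 20% gives 0.05 × 1.1% = 0.06% up to 0.20 × 23.9% = 4.8% of AEs, and only if every worsening is entered as an update.

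**The case against.** The strongest answer is that the protocol already leans towards a separate record. It makes an exacerbation an AE in itself and has OST worsening and OHT changes since Screening recorded as AEs, without excepting conditions that already have a record. A site that reads those sections this way enters the worsening with its own later onset, and the SAP rule then classes it correctly. This stands, and it makes the loss conditional. It does not remove the point, because no text requires a separate record for an open AE and Protocol 10.6 permits an update.

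A second answer is that the event stays visible elsewhere. That is also true (Step 3). But Listing 16.2.7.1 gives no by-arm counts, the death and SAE listings cover only fatal or serious events, and a withdrawal could be counted in disposition yet be missing from Listing 14.3.2.3.

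Third, the numbers are likely to be low. Eligibility is reviewed again at Visit 2, inclusion criterion 4 excludes clinically relevant abnormalities on oral examination in the investigator's opinion, and many pre-treatment AEs will have resolved by then. This stands.

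Three stronger readings are tempting, and the documents do not support them:

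- *Such events certainly drop out of the TEAE outputs.* This needs the update reading, which is permitted but not stated.
- *Up to about a quarter of AEs are misclassified.* The 24% is a share of collection time at the longest screening interval. It would be a share of misclassified AEs only if every pre-treatment AE persisted, worsened and was entered as an update.
- *The rule materially favours the products.* It applies to both arms, so background worsening is lost in both. Worsening caused by the products can occur only in the Intervention Group, so any loss of that kind would flatter them, but nothing in the documents shows that it is material. The foam is used outside the mouth and rinsed off, irritation that first appears on product is already a TEAE, and no between-arm safety test is planned.

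**Conclusion.** The point holds as a gap in the definition. SAP 4.6.1 has no worsening clause, its exclusion sentence covers every earlier onset, and neither document settles how worsening of an open AE is recorded. The class of such an event therefore turns on an unstated data-entry choice, and under one permitted choice it is missing from three TEAE tables and two TEAE listings.

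The effect on counts is probably small and cannot be derived from the documents. The only figure that they support is the window share of about 1.1% to 24%, which assumes nominal visit timing and bounds exposure rather than error. The case for a change rests on the clarity of a named safety endpoint and on the low cost of fixing it, not on a large expected number. It is worth correcting before database lock.

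**What to change.** In SAP 4.6.1:

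1. Define TEAEs as AEs with onset on or after study treatment start (randomization for the No Intervention Group), or AEs with earlier onset that increase in intensity or frequency, or become serious, on or after that date.
2. Limit the exclusion sentence to earlier-onset AEs that do not worsen in this way.
3. State one counting rule and put it in the CRF completion instructions. Either flag the original record as treatment-emergent, or enter the worsening as a separate AE with its own onset and leave the original record as non-emergent. Doing both could count one event twice in the total number of TEAEs in Table 14.3.1.1.

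The cost is a short SAP edit and a note to the site. Flagging the original record also needs the date of worsening to be available; the CRF is not in the documents, so this should be checked. The downside is a slightly higher TEAE count.

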## 8.2 Study Period

### 8.2.1 Visit 2/Day 0 – Baseline

Procedures will be conducted by the Investigator, or suitably qualified designee.

Subjects will undergo, in the following order (wherever possible), and findings documented in the CRF:

1. Changes in health, medication and non-drug treatments/procedures will be documented in the CRF.
2. Spontaneous reporting of adverse events and those elicited by asking subjects to respond to a non-leading question such as “How do you feel?” will be assessed.
3. Subject completes the questionnaire.
4. Subject removes RPD.
5. RPD is assessed for PDCI.

Property of GSK Consumer Healthcare - Confidential

May not be used, divulged, published or otherwise disclosed without the consent of GSKCH

SP1963/SOP-208661: Template Version: 14 Mar 2019

---

6. For a subset of subjects, photographic images of their RPD will be taken.
7. Subject undergoes a full OST examination.
8. Subject undergoes MGI assessment including a repeat assessment if required.
9. Subject undergoes a CI assessment.
10. Subject undergoes plaque disclosure and TPI including a repeat assessment if required.
11. Subject undergoes ODI assessment.
12. Subject undergoes BI assessment.
13. Review of the inclusion/exclusion criteria.
14. Subject eligibility assessed.
15. Subjects will be stratified and randomized to treatment group.
16. Subject's RPD will be cleaned by the study site and the subject will undergo a full sub and supra-gingival prophylaxis with confirmation of a TPI score of zero by a second suitably qualified member of site staff.
17. The subject's RPD will be returned.
18. Intervention group only - study products will be dispensed, including sundry items, product usage instructions and diary. Subject to perform supervised product usage and study staff to review instructions on correct product use with the subject for at home use.
19. No intervention group only – subject to receive only the diary.
20. All randomized subjects will receive standard oral care advice to brush their teeth twice per day with a fluoridated toothpaste, to remove their partial denture while sleeping, to clean their denture and to visit their dentist regularly.
21. AEs and incidents recorded.

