#### **4.1.1 Subject Disposition**

Screen failures will be defined as subjects who consent to participate in the clinical study but are not subsequently randomized. An enrolled subject is a subject who has signed informed consent and is eligible to proceed beyond the screening visit.

The number of subjects screened, enrolled and randomized will be presented in [Table 14.1.1](#). The number and percentage of screen failure subjects (subjects not randomized) with reasons why subjects are not randomized will also be displayed. Percentages for screen failure subjects will be based on the total number of subjects screened.

The number and percentage of subjects who complete and discontinue the study, broken down by reason for discontinuation, will be presented by treatment group and overall in [Table 14.1.1](#). The percentages will be based on the number of subjects randomized.

[Table 14.1.1](#) will also present the number and percentage of subjects in each of the defined analysis populations by treatment group and overall. Percentages will be based on the number of subjects randomized in the relevant treatment group or overall.

Subject disposition including demographic data (age, gender and race), screening date, study treatment start date (Visit 2, Day 0), the subject status (completer, Yes/No), date of study completion or withdrawal, duration (in days) in the study (defined as [(date of completion or

withdrawal – study treatment start date) + 1], the primary reason for withdrawal and further details for withdrawal will be listed ([Listing 16.2.1.1](#)).

Subject disposition information will be listed for non-randomized subjects ([Listing 16.2.1.2](#)), including demographic information (age, gender and race), screening date, reason for screen failure and any further details of reason for screen failure.

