**Table 4-1 Analysis Populations**

Population	Definition / Criteria	Analyses Evaluated
Safety	
 
All randomized subjects who receive at least one dose of the study product.
 
 
This population will be based on the study product the subject actually received.
	Safety
Modified Intent-To-Treat (mITT)	
 
All randomized subjects who received at least one dose of the study product and have at least one post-baseline efficacy measurement performed (BI, MGI, TPI, PDCI, CI, ODI).
 
 
All mITT population summaries and analyses will be presented according to the study product randomized.
	Efficacy
Per Protocol (PP)	
 
Subset of the mITT population which excludes subjects with a protocol violation that is deemed to affect efficacy for all efficacy assessments.
 
 
Subjects with a protocol violation that is deemed to affect efficacy for only some (but not all) of the efficacy assessments will be part of the PP population, but their data will be excluded from the assessment at which the protocol violation occurred.
	Efficacy analyses for BI score
Repeatability	
 
Comprise of all subjects who have a repeat clinical assessment of efficacy at any visit. There will be a separate population for repeat MGI assessment and repeat TPI assessment:           
 
MGI Repeatability population: Subjects with at least one initial and repeat assessment of MGI at any visit.
 
TPI Repeatability population: Subjects with at least one initial and repeat assessment of TPI at any visit.
 
 
 
	Repeatability analyses

The primary population for assessment of efficacy will be the Modified Intent-To-Treat (mITT) population. A PP analysis will be performed on the primary efficacy variable (BI score) only if 10% or more subjects in the mITT population are excluded from the PP population.

Any repeat clinical data collected for the repeatability assessment will only be used to assess repeatability. The main assessment of efficacy will be based on the initial assessment.

Subjects excluded from any of the analysis populations will be listed in [Listing 16.2.3.1](#).

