##### **4.3.1 Study Treatment Compliance and Exposure**

Product compliance will be recorded as the total number of brushing, mouth rinsing and denture cleaning occasions since the last visit. In addition, any missed or additional brushing, mouth rinsing or denture cleaning occasions since the last visit are collected for the Intervention Group and any deviation from the normal hygiene range or change in oral hygiene products are collected for the No Intervention Group.

Treatment exposure will be calculated for each visit interval and overall treatment duration as follows:

- Treatment Exposure (Days) = Visit Interval End Date – Visit Interval Start Date.

Compliance will be calculated for the Intervention Group for brushing, mouth rinsing and denture cleaning for each visit interval and overall as:

- Brushing/Mouth Rinsing/Denture Cleaning Compliance (%) = [(Number of Brushing/Mouth Rinsing/Denture Cleaning occasions) / (Treatment Exposure x 2)] x 100.

Overall exposure and compliance will be calculated from Visit 2 (Day 0) to Visit 4 (Week 12) [or the last available visit for subjects who discontinue prior to Visit 4 (Week 12)].

The number of brushing occasions, mouth rinsing occasions, denture cleaning occasions will be summarized by treatment group using descriptive statistics (n, mean, SD, median, minimum and maximum) for each visit interval and overall study treatment duration, in [Table 14.2.1.1.1](#) for the Safety population and [Table 14.2.1.1.2](#) for the mITT population. In addition, the percentage compliance (n, mean, SD, median, minimum and maximum) and the number and percentage of subjects <80%, between 80% - 120% and >120% compliant will also be presented for brushing, mouth rinsing and denture cleaning for the Intervention Group.

Treatment exposure (days) will be summarized by treatment group using descriptive statistics (n, mean, SD, median, minimum and maximum), for each visit interval and overall study treatment duration, in [Table 14.2.1.2.1](#) for the Safety population.

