#### **4.3.2 Prior and Concomitant Medication**

Prior or concomitant medication taken by or administered to a subject will be recorded in the case report form. The prior and concomitant medications will be coded using an internal validated medication dictionary, [CCI](#).

Prior medication and prior non-drug therapies will be listed by subject, with drug name, GSK drug synonym, reason for medication, dose, frequency, route, start date, study day relative to the study treatment start date (Visit 2) and end date ([Listing 16.2.4.4](#)). Prior medications are defined as those which stopped before the study treatment start date (Visit 2). If the stop date is unknown or incomplete and the medication cannot be considered as stopped prior to study treatment start date (Visit 2) then the medication will be considered as a concomitant medication.

Concomitant medications and concomitant non-drug therapies will be listed similarly ([Listing 16.2.4.5](#)) with either ongoing or end date displayed. Concomitant medications are defined as medications that started or stopped on or after the study treatment start date (Visit 2), or are ongoing.

For the assignment of prior and concomitant medications, the randomization date will be used as the study treatment start date for subjects randomized to the No Intervention Group.

Unknown dates will not be imputed, however if the start or stop date is unknown, then it will be assumed to be concomitant medication unless the partial start date or stop date indicates differently.

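### Does the mix of dates and date/times in the SAP's treatment-emergent rule classify Day 0 adverse events differently in the two arms?

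*SAP*

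**What the plan says.** SAP 4.6.1 states the rule in three sentences, each at a different precision.

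- The definition covers "AEs with an onset date/time on or after the study treatment start date/time (Visit 2"). Visit 2 is the only gloss on what start means; first use is not mentioned.
- The complement is that "AEs with an onset date prior to the study treatment start date/time (Visit 2) will be considered as non-treatment emergent". Here the onset is a date with no time.
- Controls have no product to start, so they get a substitute: "For the assignment of TEAEs, the randomization date will be used as the study treatment start date". This is also a date with no time.

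Elsewhere the SAP treats the start of treatment as a calendar day. Section 4.1.1 lists the "study treatment start date (Visit 2, Day 0") and counts days in the study from it. Section 4.3.1 computes "Treatment Exposure (Days) = Visit Interval End Date – Visit Interval Start Date". Section 4.3.2 makes the same substitution for controls: "For the assignment of prior and concomitant medications, the randomization date will be used as the study treatment start date".

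Protocol 8.2.1 fixes the order of events at Visit 2. The debris and bleeding indices are steps 11 and 12. At step 15, "Subjects will be stratified and randomized to treatment group". Professional cleaning of the teeth and denture is step 16, and supervised product use, in the intervention group only, is step 18. Protocol 6.2 confirms that this supervised use is the first use.

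**The concern.** Read literally, the definition asks for clock times. If a programmer took treatment start as the time of first supervised use, an intervention subject's clock would start at step 18, while a control's would start at the beginning of Day 0, because the control anchor is a date. Procedures done in both arms fall in the gap. They include the debris and bleeding assessments, which Protocol 9.2.6 and 9.2.4 describe as invasive, and the prophylaxis. An event arising from them would count as emergent in a control. In an intervention subject it would fail the definition, and the complement sentence, which tests only the onset date, would not clearly capture it either.

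TEAEs are the named safety endpoint and are tabulated by arm. A rule that leaves early events out of one column only would make the product range look comparatively better tolerated.

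**Working it through.** No figure in the plan depends on this rule, so there is nothing to reproduce. The check is to place an event at each possible point and classify it under each way the three sentences could be programmed. Only the order of the Visit 2 steps matters, not the clock times.

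**Inputs.** The order comes from Protocol 8.2.1: randomization at step 15, prophylaxis at step 16, first use at step 18. The control anchor and the definition come from SAP 4.6.1. AEs are collected from consent (Protocol 10.3.1), so Day 0 events before first use are recorded.

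**Rule.** Emergent = onset on or after the anchor. Entries are intervention / control.

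| Event position | (a) Dates in both arms | (b) First-use time; randomization date | (c) First-use time; randomization time | (d) Randomization time in both arms |
|---|---|---|---|---|
| Day -1 | no / no | no / no | no / no | no / no |
| Day 0, steps 1-14 | yes / yes | no* / yes | no* / no | no / no |
| Day 0, steps 15-17 | yes / yes | no* / yes | no* / yes | yes / yes |
| Day 0, step 18 on | yes / yes | yes / yes | yes / yes | yes / yes |
| Day 1 | yes / yes | yes / yes | yes / yes | yes / yes |
| Day 0 windows where the arms differ | 0 of 3 | 2 of 3 | 1 of 3 | 0 of 3 |

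*Fails the defining sentence. The complement sentence tests an onset date, and a Day 0 onset date is not before the Visit 2 date, so the event is arguably unclassified rather than non-emergent.

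**Which column do the documents support?** Column (b) needs two things.

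1. Treatment start must mean the clock time of first use. No section says so. SAP 4.1.1 gives a day, SAP 4.3.1 and 4.3.2 calculate with dates, and the control sentence in 4.6.1 itself refers to a start date without a time.
2. AE onset times and first-use times must exist in the data. Protocol 8.1.1.1 sends the time of consent to the CRF, but neither document describes an onset time or a first-use time being recorded. Protocol 10.4.2 asks for a date of onset on the SAE form.

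Without those times only column (a) can be programmed. Randomization and first use both belong to Visit 2, so the two anchors are then the same day.

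**Direction, if (b) were programmed.** Compare (a) with (b) over the three Day 0 windows.

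- Control: yes, yes, yes under (a); yes, yes, yes under (b). No change.
- Intervention: yes, yes, yes under (a); no, no, yes under (b). Two windows drop out.

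Relative to the date rule, the effect would be a lower intervention count, not a higher control count.

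**Size.** The documents give no Day 0 event rate, so no total follows. For the unit only: Protocol 5.1 plans equal groups, so 150 / 2 = 75 per arm. Each intervention subject whose only AE fell on Day 0 before first use would lower that arm's proportion by 1 / 75 = 1.3 percentage points.

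**The case for a change.** The strongest reply is that the defining sentence is faulty either way. If times are not collected, it cannot be applied as written; if they are, and start means first use, it treats the arms unequally in a direction that favours the product. The Day 0 interval is not empty. Besides probing and prophylaxis, the soft tissue examination is step 7, and Protocol 9.3.1 records a worsening since Screening as an AE, which could be given a Day 0 onset. Aligning the sentences would cost a line or two of the SAP.

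Much of this stands. The wording is uneven, the interval is real, and under column (b) the direction would be as described. What does not stand is the step from uneven wording to a different result. If times are missing, the analyst falls back on dates, and the arms are treated alike. If times turn out to be in the eCRF, which cannot be checked from these documents, the programmer would still have to set aside the date convention used for the same concept in three other SAP sections to produce the asymmetry.

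The consequences are also limited. SAP 4.6.1 plans counts and percentages with no test, lists every AE for all randomized subjects, and has all AEs reviewed before database lock. Protocol 10.1 excludes expected signs of the disease under study from AEs.

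A separate wording point touches the same tables: SAP Table 4-1 defines the Safety population as "All randomized subjects who receive at least one dose of the study product", which controls never receive. The control rule in 4.6.1 presupposes that controls are in the TEAE tables. That definition is a different question and does not alter the conclusion here.

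**Conclusion.** No change to the plan is needed. SAP 4.6.1 is loosely worded, but under the date convention used in the rest of the SAP both arms are anchored on the Visit 2 date and no Day 0 event is classified differently (0 of 3 windows). Rewriting the sentences in dates would give the same tables.

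The conclusion rests on two assumptions: that the analysts carry the convention of SAP 4.1.1, 4.3.1 and 4.3.2 into 4.6.1, and that controls are counted in the safety tables, as 4.6.1 implies. If instead first-use times were programmed against the control's randomization date, 2 of 3 Day 0 windows would differ, through events omitted or left unclassified in the intervention arm. The number cannot be derived from the documents, and the events would still appear in the AE listing. The date rule has one cost: Day 0 events before any product use are labelled emergent. It applies equally to both arms, which is a fair trade for a rule that needs no clock times.
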